7.2.2. Secondary Objectives

Secondary Objectives	Parameter Description	Parameter Formula		Abbreviated Description
4. To characterize the diagnostic performance of imaging of PD G 506 A to identify malignant breast tissue (Arm 2 only)	Orientation-level diagnostic performance of PD G 506 A-induced fluorescence to determine the presence or absence of residual cancer in the surgical cavity at the end of SoC as	P(2.4) Sensitivity = TP Orientation TP Orientation + FN Orientation	x 100%	Orientation level diagnostic performance to identify carcinoma with FGR after SoC
	compared to the final margin histopathology.	P(2.4) Specificity = TN Orientation TN Orientation + FP Orientation	x 100%	
		P(2.4) PPV = TP Orientation TP Orientation + FP Orientation	x 100%	
		P(2.4) NPV = TN Orientation TN Orientation + FN Orientation	x 100%	
5. To characterize the diagnostic performance of imaging of PD G 506 A to identify malignant breast tissue	Orientation-level diagnostic performance of PD G 506 A-induced fluorescence to determine the presence or absence of residual cancer in the	$P(2.5) Sensitivity = \frac{TP \ Orientation}{TP \ Orientation + FN \ Orientation}$	x 100%	Orientation level diagnostic performance to identify carcinoma at the end of FGR
(Arm 2 only)	surgical cavity at the end of FGR as compared to the final margin histopathology.	P(2.5) Specificity = TN Orientation TN Orientation + FP Orientation	x 100%	

SBI-CIP 20-002 Rev: v1.8 A prospective multi-center clinical study evaluating the use of PD G 506 A and the Eagle V1.2 Imaging System for the visualization of carcinoma during breast conserving surgery	Page: 32 of 157
---	-----------------

Secondary Objectives	Parameter Description	Parameter Formula		Abbreviated Description
		$P(2.5) \text{ PPV} = \\ \\ \frac{\textit{TP Orientation}}{\textit{TP Orientation}}$	x 100%	
		$P(2.5) \text{ NPV} = \\ \frac{TN \text{ Orientation}}{TN \text{ Orientation}}$	x 100%	
6. To characterize the diagnostic performance of imaging of PD G 506 A to identify malignant breast tissue (Arm 2 only).	Patient-level sensitivity of PD G 506 A-induced fluorescence (following SoC BCS) to determine the presence or absence of residual cancer in the surgical cavity at the end of FGR as compared to the final margin histopathology.	P(2.6) Sensitivity = TP Patient TP Patient + FN Patient	x 100%	Patient-level sensitivity to identify residual carcinoma after FGR is complete.

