to identify malignant breast tissue (Arm 2 only).	determine the presence or absence of residual cancer in the surgical cavity at the end of FGR as compared to the final margin histopathology.	P(2.13) Specificity = TN Patient TN Patient + FP Patient	x100%	identify residual carcinoma after FGR is complete.
	Only FL-positive orientation-in vivo and FL-negative orientation-in vivo orientations are included in the patient- level diagnostic performance	$\frac{P(2.13) \text{ PPV} =}{\text{TP Patient } (in \ vivo)}$ $\frac{\text{TP Patient } (in \ vivo) + \text{FP Patient } (in \ vivo)}{\text{TP Patient } (in \ vivo)}$	x100%	
	definitions for this analysis. FL-assessment of in vivo tissue in the final cavity will be compared to histopathological status of final margins of the ex vivo tissue specimens.	$\frac{P(2.13) \text{ NPV} = \frac{\text{TN Patient } (in \ vivo)}{\text{TN Patient } (in \ vivo) + \text{FN Patient } (in \ vivo)}$	x100%	
14. To determine the frequency with which fluorescence is found only on one of the opposing surfaces in an orientation.	Percentage of orientations where in vivo FL imaging disagrees with ex vivo FL imaging (e.g., FL-negative cavity surface but FL-positive corresponding shave or specimen margin surface, or vice versa). FL imaging at all points during the surgery (not just at the end) are used for this endpoint.	P(2.14) = # orientations where FL status of Orientation-in vivo is discordant with FL status of Orientation-ex vivo All Orientations	x100%	Percentage of orientations with discordant FL status.
15. To characterize the impact of FGR on the rate of 2 nd surgery within 1 year	Percentage of patients receiving a 2 nd surgery on the ipsilateral breast within 1 year of index BCS to remove	P(2.15a) Arm 1 only =	x100%	Patient-level re-operation rate due to suspected residual disease.

SBI-CIP 20-002 Rev: v1.8 A prospective multi-center clinical study evaluating the use of PD G 506 A and the Eagle V1.2 Imaging System for the visualization of carcinoma during breast conserving surgery	Page: 37 of 157
---	-----------------

Secondary Objectives	Parameter Description	Parameter Formula		Abbreviated Description

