7.3. Exploratory Objectives and Endpoints

Exploratory Objective	Parameter Description	Parameter Formula		Abbreviated Description
19. To characterize the	Patient-level ex vivo diagnostic	P(E.19) Sensitivity =		Patient-level ex vivo specificity to
diagnostic performance	performance of PD G 506 A-induced	TP Patient (ex vivo)	x 100%	identify residual carcinoma after
of ex vivo imaging of	fluorescence to determine the	TP Patient (ex vivo) + FN Patient	X 100%	FGR is complete.
PD G 506 A to identify	presence or absence of residual	(ex vivo)		

SBI-CIP 20-002	Rev: v1.8	A prospective multi-center clinical study evaluating the use of PD G 506 A and the Eagle V1.2 Imaging System for the visualization of carcinoma during breast conserving surgery	Page: 39 of 157
-----------------------	--------------	--	-----------------

Exploratory Objective	Parameter Description	Parameter Formula		Abbreviated Description
malignant breast tissue (Arm 2 only).	cancer in the surgical cavity at the end of FGR as compared to the final margin histopathology.	P(E.19) Specificity = TN Patient (ex vivo) TN Patient (ex vivo) + FP Patient (ex vivo)	x 100%	
	Only FL-positive orientation- ex vivo and FL-negative orientation- ex vivo orientations are included in the patient-level diagnostic performance	P(E.19) PPV = TP Patient (ex vivo) TP Patient (ex vivo) + FP Patient (ex vivo)	x 100%	
	definitions for this analysis.	P(E.19) NPV = TN Patient (ex vivo) TN Patient (ex vivo) + FN Patient (ex vivo)	x 100%	
20. To determine the frequency with which PD G 506 A-induced fluorescence is visualized but that tissue is not resected	Percentage of patients who did not have a FL-guided shave although indicated by FL imaging.	P(E.20a) = #Patients with ≥ 1 FL-positive orientation where no FL- driven shave was resected #Patients with ≥1 FL-positive orientation	x 100%	Fluorescence-positive tissue that cannot be resected.
(Arm 2 only).		P(E.20b) = #Patients with ≥ 1 FL-positive orientation where no FL- driven shave was resected #Patients in Arm 2	x 100%	
		P(E.20c) Clinical outcomes (e.g., porfinal margin rate, need for 2 nd surger also be reported for patients ≥ 1 FL-1 orientation but the FL-driven shave(s resected	y) will positive	

SBI-CIP 20-002	Rev: v1.8	A prospective multi-center clinical study evaluating the use of PD G 506 A and the Eagle V1.2 Imaging System for the visualization of carcinoma during breast conserving surgery	Page: 40 of 157
-----------------------	--------------	--	-----------------

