- If ≥1 are classified as FL-positive, the *surgeon* will then resect a *FL-driven cavity shave* specimen for each cavity surface where either the *final cavity surface after SoC* and/or the corresponding *final margin after SoC* was identified as FL-positive.

The *surgeon* will then perform FL imaging of the inside and outside surface of all *FL-driven cavity shave specimens* resected in the previous step and the corresponding *cavity surfaces*. The *surgeon* will verbalize which (i.e., S, M, P, L, I, A), if any, of the inside and outside surfaces of the *FL-driven cavity shave specimens* and corresponding *cavity surface(s)* is considered positive for carcinoma based on the visualization of red PpIX FL (i.e. FL-positive).

The FL-status of each *specimen surface* and *cavity surface* will be recorded in the Intraoperative Data Collection Tool.

- If none are classified as FL-positive, the *surgeon* will verbalize the completion of Eagle V1.2 Imaging System assessment.
- If ≥1 are classified as FL-positive, the *surgeon* will continue to perform *FGR* as described above until such time that either no red PpIX FL is detected on both the outside surface of the last round of *FL-driven cavity shave specimens* and *surgical cavity* or until no further tissue can be removed based on the *surgeon's* best clinical judgment and in the interest of best medical practice for the patient.
- If at the completion of Eagle V1.2 Imaging System assessment, red PpIX FL is still observed on the *final margins after FGR* and/or in the *surgical cavity* and no further resection is performed, the anatomical surface(s) of residual fluorescence (i.e., S, M, P, L, I, A) and the reason for not performing further *FGR* will be recorded.

The *surgeon* will then complete the procedure as per SoC and all samples will be sent for histopathological assessment.

In order to maintain the blinding of the individuals responsible for processing and evaluating the specimens (e.g. pathologist's assistant, pathologist) the conditions under which the *cavity shave specimens* were resected will not be indicated in the labelling.

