15.2. Sample Size Estimation

The sample size of Part A has been chosen on pragmatic grounds to be approximately 75 study patients. The number of patients ultimately included in Part A will be decided by the Steering Committee and the Sponsor based on the perceived understanding of the protocol by clinical sites and the feedback obtained during the Part A training phase. Part A will not be randomized; all study patients in Part A will receive PD G 506 A. Data acquired from Part A will be used to confirm the Investigators' understanding of fluorescence guided resection (FGR) procedures in the protocol and to confirm the sample size for Part B. Only data from participants in Part B will be used for the analyses of primary and secondary efficacy. Data from all patients in both Part A and Part B will be used for the evaluation of safety and analyses will include assessments of data from Part A and Part B separately, as well as all study patients (Part A and Part B together).

P(1.1) Conversion Rate among all patients =

patients with at least one histopathology-positive margin following SoC and histopathology negative final margins after FGR

All patients imaged (Arm 2)

SBI-CIP 20-002 Rev: v1.8 A prospective multi-center clinical study evaluating the use of PD G 506 A and the Eagle V1.2 Imaging System for the visualization of carcinoma during breast conserving surgery	Page: 96 of 157
---	-----------------

The sample size in Part B of the study is only driven by the primary endpoint P(1.1). The primary endpoint is intended to determine the percentage of patients with at least one histopathology-positive margin after SoC who then have all histopathology-negative margins after FGR (conversion rate among all patients in Arm 2). To demonstrate benefit, the point estimate P(1.1) must be statistically significantly greater than 1%. By meeting this primary endpoint, we will demonstrate that FGR adds clinical benefit above and beyond what is achieved with SoC.

Based on the expected 3% conversion rate estimate for P(1.1), a total of 500 patients will be required in Part B of the study to demonstrate statistical significance at a Type 1 error level of 0.05 with 90% power using a 2-sided Z test for a binomial proportion assuming a null hypothesis proportion of 1%.

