Using a randomization ratio of 1:6 (Arm 1-SoC; Arm 2: PD G 506 A), a total sample size of 525 patients (Arm 1: N=72; Arm 2: N=428) would be required, accounting for a 5% loss to follow-up. The primary efficacy analysis will be based on the mITT (modified intention-to-treat population), which includes all Part B patients randomized to Arm 2 who undergo surgery and have recorded surgical histopathology data.

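### Sensitivity and specificity at the end of FGR (P(2.5), P(2.6), P(2.13), P(E.19)) are scored on surfaces that the stop rule clears of fluorescence, so they mix accuracy with stopping behaviour and cannot be read as detection accuracy

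*Combined protocol and SAP*

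**What the plan says.** **The endpoints.** P(2.6) in section 7.2.2 is described as "Patient-level sensitivity to identify residual carcinoma after FGR is complete", with a matching specificity. P(2.5) gives sensitivity, specificity, PPV and NPV by orientation at the same time point. P(2.13) gives the same four measures by patient from in vivo imaging, to detect "residual cancer in the surgical cavity at the end of FGR as compared to the final margin histopathology". P(E.19) in section 7.3 does so for ex vivo imaging, again for "cancer in the surgical cavity at the end of FGR as compared to the final margin histopathology". The stated objective in each case is to characterise diagnostic performance.

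**The stop rule.** Section 12.4.3 has the surgeon repeat fluorescence-guided resection "until such time that either no red PpIX FL is detected on both the outside surface of the last round of" fluorescence-driven shaves and in the cavity, or until no more tissue can be removed in the surgeon's clinical judgement. Appendix 2 Steps 25-27 repeat this. Under Appendix 2 an orientation gets no fluorescence-driven shave when cavity and specimen are both negative at the end of SoC, or when a shave is not possible.

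**The surfaces scored.** Section 15.4.4, in its text on completion of FGR and BCS, takes fluorescence from the final cavity and from the outside surface of the last specimen at each orientation. The reference is the histology of that outside surface.

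**Residual fluorescence.** Where it remains, its location and the reason for stopping are recorded (12.4.3). P(E.20) counts patients with a positive orientation from which no fluorescence-driven shave was taken.

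**The concern.** The surfaces that end the resection are the surfaces on which accuracy is then scored. Once the rule has been followed, an orientation can be called positive only if fluorescence was seen and left. The true-positive and false-positive cells are therefore largely emptied before scoring. The false-negative cell is not, because a margin containing cancer that did not fluoresce stays where it is.

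Sensitivity then falls and specificity rises for a reason unrelated to how well the agent marks cancer. A reader of the study report could take the low sensitivity as failure of the agent, or the high specificity as strong performance. P(2.13) and P(E.19) are also the plan's only patient-level in vivo and ex vivo accuracy endpoints, so the patient-level comparison of the two imaging modes is made only where it tells least. Sections 7.2.2, 7.3 and 15.7 carry no caveat.

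**Working it through.** **The plan's own figure.** No sample size, power or expected value is given for these four endpoints. The only related figure is the Arm 2 size of 428, used below as a denominator. Section 15.2 states: "Based on the expected 3% conversion rate estimate for P(1.1), a total of 500 patients will be required in Part B", with two-sided 0.05, 90% power and a 1% null rate. It reproduces:

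n = [(1.960 × √(0.01 × 0.99) + 1.2816 × √(0.03 × 0.97)) / 0.02]² = 428; 428 × 7/6 ≈ 500; 500 × 1.05 = 525.

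**Inputs for the check**
- s = 70% and 1 − f = 80%: true sensitivity and specificity per look. These are the values that section 15.6.2 expects to be exceeded at the end of SoC.
- u: share of fluorescence-positive sites left in place. Not in the documents; assumed 0% to 20%, independent of cancer status.
- 20% margin-positive after SoC: an assumption, consistent with the plan's expected 3% conversion overall and 15% among SoC-positive patients (3/15 = 20%).
- 30% still positive after a shave: an assumption.
- One site per patient, with the same accuracy at each look.

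**Formulas.** At every look a cancer-positive site ends as a true positive with probability s·u, ends as a false negative with probability 1 − s, or is shaved and imaged again. The first two keep the same ratio in each round, so

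end-of-FGR sensitivity = s·u / (s·u + 1 − s).

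By the same argument, end-of-FGR specificity = (1 − f) / (1 − f + f·u).

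Neither depends on the 20% or the 30%. PPV, NPV and the counts do.

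**Example, u = 10%.** Sensitivity = 0.07 / (0.07 + 0.30) = 18.9%. Specificity = 0.80 / (0.80 + 0.02) = 97.6%.

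| u | Sensitivity | Specificity | PPV | NPV | FL-positive of 428 |
|---|---|---|---|---|---|
| 0% | 0% | 100% | undefined | 92.4% | 0 |
| 2% | 4.5% | 99.5% | 43.5% | 92.4% | 3.5 |
| 5% | 10.4% | 98.8% | 43.6% | 92.4% | 8.6 |
| 10% | 18.9% | 97.6% | 43.8% | 92.3% | 16.9 |
| 20% | 31.8% | 95.2% | 44.1% | 92.2% | 32.6 |
| 100% (nothing resected) | 70.0% | 80.0% | 46.7% | 91.4% | 128.4 |

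The last row is the accuracy before the rule acts.

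**Does the true accuracy still show?** At u = 10%, a true sensitivity of 50%, 70% or 90% reads as 9%, 19% or 47%. A true specificity of 70%, 80% or 90% reads as 96%, 98% or 99%. At u = 0, sensitivity is 0% for any s below 1.

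**The case against.** **These endpoints decide nothing.** Only P(1.1) makes the study positive (15.6). The four endpoints have no hypothesis or threshold, and P(E.19) is exploratory. This stands, and it limits the severity.

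**Accuracy is already measured before the rule acts.** P(2.2), P(2.3), P(2.4) and P(2.7) use the end of SoC. The Amendment 5 history records that specificity, then a primary endpoint, was moved there from the end of FGR on FDA recommendation. This also stands. A reader might infer that the trial's tested accuracy evidence is compromised; the documents do not support that.

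**The rule has an exception.** A reader might infer that the figures are wholly fixed by the rule, so that a good and a poor agent look alike. That is exact only if no fluorescence is left. Sections 6.2.6 and 12.4.3 allow the surgeon to stop with fluorescence present, and the plan records such cases. The 9%, 19% and 47% above show that sensitivity still varies with the agent, though far from its true value.

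**PPV is not set by the rule.** In the model it hardly moves with u and lies near its end-of-SoC value. This stands: the trouble with PPV is small, selected numbers, and P(2.6) has no PPV at all.

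**Other in vivo and ex vivo endpoints exist.** P(2.14) covers discordance between the two modes, and P(E.27) covers ex vivo accuracy. Both work by orientation, so the patient-level gap remains.

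**P(2.5) should not simply be withdrawn.** The amendment history says it was raised to secondary on FDA recommendation. Relabelling is therefore the safer course.

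**Conclusion.** The point holds in this form. End-of-FGR sensitivity is pushed towards 0% and specificity towards 100%, because fluorescence-positive sites are removed before scoring. With a true 70%/80% and 5% to 10% of positive sites left in place, the reported figures would be about 10% to 19% and 99% to 98%. The direction follows from the plan's text alone. The size depends on u, which the documents do not give, and on u being unrelated to cancer status.

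PPV in P(2.5), P(2.13) and P(E.19) is undefined if nothing is left. Otherwise it rests on about 3.5 to 17 patients of 428 when u is 2% to 10%, all with tissue that was not resected. NPV and P(2.9) stay interpretable because the rule does not empty the fluorescence-negative group. The primary endpoint and the tested P(2.2) and P(2.3) are untouched. Severity is moderate: should be fixed.

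**What to change.** 1. **Move P(2.13) and P(E.19) to the initial assessment at the end of SoC.** Compare fluorescence of the final cavity after SoC (in vivo), or of the last SoC outside surface (ex vivo), with the histology of the last SoC outside surface. Every orientation has that reference, so the two modes are judged on equal terms. Show alongside it the reference in section 15.4.4.1, which adds the inside surface of the first fluorescence-driven shave where one was taken. This keeps the results consistent with P(2.2) and P(2.3) and retains the direct histology of the imaged cavity surface.

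2. **At the end of FGR, rely on NPV and P(2.9).** P(2.9a) already gives the share of fluorescence-clear patients with a positive final margin, and 1 − NPV in P(2.5) gives the orientation-level version. If sensitivity and specificity in P(2.5) and P(2.6), and PPV in P(2.5), are kept because of the FDA recommendation, state in the SAP and in table footnotes that they are conditional on the stop rule and are not detection accuracy. Report beside them the number of patients and orientations with residual fluorescence.

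**Cost.** Two endpoints are re-timed, which may need regulatory notice. The rest is wording and table layout. The fluorescence and histology needed are already recorded under sections 12.4.3 and 12.6.1, so no new data are required. The change should be made before database lock.
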